#### 2.1.2 Secondary Objectives

The secondary objectives of this study are:

1. To assess further PK parameters including apparent total clearance, terminal half-life and apparent volume of distribution \*
2. To assess the safety and tolerability of different zamicastat doses
3. To investigate the effect of different zamicastat doses on plasma dopamine  $\beta$  hydroxylase (D $\beta$ H) activity\*
4. To investigate the effect of different zamicastat doses on urinary catecholamine levels (norepinephrine and dopamine)\*
5. To investigate the change in pulmonary haemodynamic parameters
6. To investigate the change in the 6-minute walk test (6-MWT)
7. To investigate the change in biomarkers
8. To investigate the change in cardiac structure and contractibility, assessed by echocardiography
9. To investigate the change in quality of life, assessed by SF-36v2

\* Covered in a reporting and analysis plan prepared by Quotient Sciences Ltd. (Appendix 4).

### 2.2 Study Endpoints

#### 2.2.1 Primary Endpoint

The following PK parameters (24-hour profile) for zamicastat and its metabolites will be derived after a single dose of 50 mg zamicastat at visit A1 (Day 1):

1. Area under the curve 0-24 h ( $AUC_{0-24h}$ )
2. Maximum plasma concentration ( $C_{max}$ )
3. Time until  $C_{max}$  ( $t_{max}$ )

The following PK parameter (24-hour profile) for zamicastat and its metabolites will be derived at steady-state at the individual HTD and will be taken at visit MPV3:

4. Area under the curve 0-24 h ( $AUC_{0-24h,SS}$ )
5. Maximum plasma concentration ( $C_{max,SS}$ )
6. Time until  $C_{max,SS}$  ( $t_{max,SS}$ )
7. Minimum plasma concentration at the end of the dosing interval ( $C_{min,SS}$ )

The following PK parameter (trough level) will be derived for each dose at steady-state (visits A3, B3, C3, D3, MPV1, MPV2, MPV3).

8. Minimum plasma concentration at the end of the dosing interval ( $C_{min,SS}$ )

The analysis of PK parameters is covered in a reporting and analysis plan prepared by Quotient Sciences Ltd. (Appendix 4).

## 2.2.2 Secondary Endpoints

### 2.2.2.1 Safety Endpoints

The safety endpoints of this study are:

1. Adverse events
2. Clinically relevant changes in laboratory parameters (haematology, biochemistry, coagulation, urinalysis, arterial blood gas analysis)
3. Clinically relevant changes in vital signs
4. Clinically relevant changes in physical examination
5. Clinically relevant changes in ECG
6. Number of digital scars (only in patients with scleroderma)
7. Skin score (only in patients with scleroderma)

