10.3 Selection of Doses in the Study

10.3.1 Selection and timing of dose for each patient

Each patient will start treatment with 50 mg zamicastat once daily (Dose A) at visit A1 and will be up-titrated step by step to the individual HTD i.e. up to 200 mg zamicastat once daily. The 100 mg tablet has to be split at the break score in two equal halves using a pill splitter.

Table 2: Dosage regimen

	Daily dose
Dose A	50 mg (half a tablet of 100 mg)
Dose B	100 mg (one tablet of 100 mg)
Dose C	150 mg (one and a half tablet of 100 mg)
Dose D	200 mg (two tablets of 100 mg)

Each next dose will start after 14 days of treatment if the previous dose was considered safe by the investigator. The up-titration is based on the following safety criteria, including but not limited to:

- Absence of symptomatic and/or clinically relevant orthostatic hypotension
- SBP > 95 mmHg or DBP > 50 mmHg
- Absence of clinically significant changes in ECG parameters (heart rate, P-R interval, QRS duration, QT and QTc interval)
- Absence of clinically significant hypersensitivity/skin allergic reactions

Patients not fulfilling the criteria for up-titration after 14 days of treatment with 50 mg zamicastat have to be withdrawn from the trial.

If the patient's next dose will not be tolerated by the patient, the dose has to be down-titrated to his/her previous dose and this dose will be considered as the individual HTD, if tolerated by the patient. Treatment at the individual HTD will be for 42 days during the maintenance period.

Zamicastat has to be taken in the morning after breakfast. The patient must not take the tablet at home on visit days (A3/B3/C3/D3, MPV1, MPV2 and MPV3).

In case a patient missed to take the dose after breakfast, (s)he should take the dose after lunch. The next dose should be taken as scheduled. If the dose was missed after lunch too, the dose for this day has to be skipped.

Patients taking 150 mg or 200 mg of zamicastat and who will not participate in the extension study will take 100 mg zamicastat for 14 days.

In case a patient will discontinue the trial early due to the occurrence of an AE, down-titration is not mandatory, but at the investigator's discretion. In case down-titration is recommended by the investigator, it should follow the same procedure as described above.

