13.4.3 Analysis of secondary safety endpoints

All safety analyses will be based on the SS. Treatment-emergent AEs will be summarised by Medical Dictionary for Regulatory Activities (MedDRA) primary system organ class (SOC) and preferred term (PT).

In addition, TEAEs will be summarised by severity and drug relationship. TEAEs leading to discontinuation from the study, AEs of special interest and serious TEAEs will be summarised in addition. All AEs will be listed.

Laboratory, vital signs and ECG parameters will be described using summary statistics. The incidence of clinically relevant abnormalities in laboratory and ECG results will be described using frequency counts and percentages.

The number of digital scars and skin score in patients with scleroderma will be analysed using summary statistics.

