### 4.1 General Methodology and Presentation of the Results

The default summary statistics for quantitative (continuous) variables will be

- the number of patients (n),
- mean,
- standard deviation (SD),
- coefficient of variation (%CV),
- median,
- minimum (min) and maximum (max)

for patients with data.

Mean and median will be presented to one more decimal place than the raw value. The minimum and maximum values will be presented with the same decimal precision as the raw value. SD will be reported to two decimal places greater than the original value, however no more than 3 decimal places will be presented. CV will be reported to one decimal place.

For qualitative (categorical) variables, the frequency count (n) and percentage (%) of patients with non-missing data per category will be the default frequency tabulations. Where appropriate and present, the number of missing values will be displayed as “Missing” category.

Percentage values are to be presented to one decimal place, for example, 52.3%.

The denominator used for calculation of the percentages will be specified in a footnote to the tables for clarification.

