### **5.6.4 Vital Signs**

Vital signs will be collected at screening (V1), visits A1, A3/B3/C3/D3, MPV1, MPV2, MPV3/EDV and FUV2. Blood pressure and heart rate will be measured in supine position (two measurements) and afterwards in standing position (one measurement). Tympanic body temperature will also be assessed.

At visits A1 and MPV3, blood pressure and heart rate will be measured before IMP intake as well as 4, 8 and 24 hours after IMP intake. For patients enrolled under protocol version final 1.0, vital signs were only evaluated before IMP intake.

Systolic and diastolic blood pressure and pulse rate will be summarised by measurement position. The mean value of measurements in the supine position at a given timepoint will be used in summaries. **Orthostatic changes** in vital sign parameters will also be calculated as the difference between the measurement in the standing position and the mean of the supine measurements. The orthostatic changes will be displayed after each corresponding parameter's standing position results in summaries.

To evaluate the short-term effects of the IMP on vital sign parameters, the absolute change from the pre-dose value within the corresponding visit will be calculated for each parameter at visits A1 and MPV3. Additionally, the difference in the within-visit changes will be evaluated for each corresponding timepoint between visits MPV3 and A1.

**Physical measurements** – height and weight will be assessed at visit V1. Weight will also be measured at MPV3/EDV. BMI will be calculated from available data (see Section 5.2.1 for calculation).

The following statistical output will be provided:

Table 15.3.4.1.1 Summary of Vital Signs by HTD– Safety Set

Table 15.3.4.1.2 Summary of Vital Signs – Safety Set

Vital sign parameters will be summarised including change from baseline at each timepoint by HTD and overall.

Table 15.3.4.2 Summary of Vital Signs by Pooled HTD – Safety Set

Vital sign parameters will be summarised as above, with HTD pooled into “HTD < 200 mg” and “HTD 200 mg” groups.

Table 15.3.4.3.1 Summary of Short-Term IMP Effect on Vital Signs by HTD – Safety Set

Table 15.3.4.3.2 Summary of Short-Term IMP Effect on Vital Signs – Safety Set

The observed values and absolute changes from the pre-dose value will be summarised for each vital sign parameter at each timepoint by HTD and overall.

Table 15.3.4.4.1 Summary of Change in Short-Term IMP Effect on Vital Signs by HTD – Safety Set

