Table 15.3.4.4.2 Summary of Change in Short-Term IMP Effect on Vital Signs – Safety Set

The changes from pre-dose values and the differences in changes from pre-dose values will be summarised between corresponding timepoints at visits A1 and MPV3 by HTD and overall.

Table 15.3.4.5.1 Summary of Physical Measurements by HTD – Safety Set

Table 15.3.4.5.2 Summary of Physical Measurements – Safety Set

Physical measurements will be summarised including change from baseline at each timepoint by HTD and overall.

Figure 15.3.1 Vital Signs Median Change from Baseline – Safety Set

The median changes from baseline of vital signs parameters at each post-baseline timepoint will be displayed by will be displayed by HTD. The HTD will be pooled into “HTD < 200 mg” and “HTD 200 mg” groups.

Listing 16.2.4.4 Vital Signs and Physical Measurements – Enrolled Set

Values of vital signs and physical measurements will be listed.

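### No vital-signs output counts patients with a clinically relevant change, although that is how the safety endpoint is worded

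*SAP*

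**What the plan says.** The endpoint in SAP 2.2.2.1 is "Clinically relevant changes in vital signs". It is listed apart from adverse events, and Protocol 13.1.2.1 lists the same endpoint.

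The planned vital-signs outputs in SAP 5.6.4 are:

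- Tables 15.3.4.1.1 and 15.3.4.1.2: "Vital sign parameters will be summarised including change from baseline at each timepoint by HTD and overall". Table 15.3.4.2 repeats this with HTD pooled into two groups.
- Orthostatic differences, described as follows: "in vital sign parameters will also be calculated as the difference between the measurement in the standing position and the mean of the supine measurements". They appear in the same summaries.
- Tables 15.3.4.3.1 and 15.3.4.3.2: "The observed values and absolute changes from the pre-dose value will be summarised for each vital sign parameter at each timepoint by HTD and overall". Tables 15.3.4.4.1 and 15.3.4.4.2 compare those within-visit changes between A1 and MPV3.
- Figure 15.3.1: "The median changes from baseline of vital signs parameters at each post-baseline timepoint will be displayed", by pooled HTD.
- Listing 16.2.4.4: individual values.

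SAP 4.1 fixes the content of a continuous summary. "The default summary statistics for quantitative (continuous) variables will be" n, mean, SD, %CV, median, minimum and maximum.

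Protocol 13.4.3 plans summary statistics for laboratory, vital signs and ECG parameters, then adds: "The incidence of clinically relevant abnormalities in laboratory and ECG results will be described using frequency counts and percentages". Vital signs are not in that second sentence.

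**The concern.** The endpoint asks whether patients had a clinically relevant change. That calls for a criterion and a count, and SAP 5.6.4 has neither: it sets no threshold and describes no investigator rating of clinical significance. The sections on laboratory tests, blood gases, ECG and physical examination all describe such a rating and tabulate it.

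Blood pressure matters in this trial. Protocol 10.8.3 warns of orthostatic hypotension and syncope. Protocol 10.3.1 includes "SBP > 95 mmHg or DBP > 50 mmHg" among the up-titration criteria. Deviations from those criteria (PD#24 in SAP 6) are pre-classed as minor, so under that class they stay out of the major-deviations table. A small average fall can coexist with a handful of patients who had a large one, and the vital-signs outputs would not show how many.

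**Working it through.** The documents give no figure to reproduce, and the sample size of 32 was not formally calculated. The check has four steps.

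**1. Outputs side by side** (SAP 5.6.2 to 5.6.6 and the output lists in SAP 10)

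| Assessment | Patient counts (n, %) planned |
|---|---|
| Haematology, biochemistry, coagulation | Yes: Tables 15.3.2.2.1 to 15.3.2.2.3, with clinically significant low and high |
| Urinalysis | Yes: Table 15.3.2.2.4 |
| Blood gases | Yes: Tables 15.3.3.2 and 15.3.3.3 |
| ECG | Yes: Tables 15.3.5.4.1 to 15.3.5.4.3 |
| Physical examination | Yes: Table 15.3.6 |
| Vital signs | None in Tables 15.3.4.1.1 to 15.3.4.4.2, Figure 15.3.1 or Listing 16.2.4.4 |

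**2. Can the count be recovered from the planned statistics?** Sets of n = 32 integer changes (mmHg) were searched for with target mean -4, SD 12, median -3, minimum -30 and maximum 25, fixing the number of changes at or below -20. These values and the 20 mmHg cut-off are illustrative assumptions.

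| Falls of 20 or more | Mean | SD | Median | Min | Max |
|---|---|---|---|---|---|
| 1 | -4.00 | 12.02 | -3 | -30 | 25 |
| 2 | -4.00 | 11.99 | -3 | -30 | 25 |
| 3 | -4.03 | 11.99 | -3 | -30 | 25 |
| 4 | -4.03 | 12.00 | -3 | -30 | 25 |
| 5 | -4.00 | 12.00 | -3 | -30 | 25 |
| 6 | -4.00 | 12.02 | -3 | -30 | 25 |

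The summaries are practically the same while the count varies from 1 to 6, so the planned tables do not determine it.

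**3. Illustrative size.** The documents give no baseline SBP or SD. Assume baseline mean 115, SD 15, a mean fall of 5 mmHg and a normal distribution, with P(SBP < 95) = Φ((95 - mean)/SD).

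- Before: Φ((95 - 115)/15) = Φ(-1.33) = 9.1%, or 2.9 of 32.
- After: Φ((95 - 110)/15) = Φ(-1.00) = 15.9%, or 5.1 of 32.
- Increment: 6.8 percentage points, or 5.1 - 2.9 = 2.2 patients of 32.

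Exclusion criterion 2 removes patients with repeated low readings at V1, so an untruncated normal probably overstates the share already low at baseline.

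**4. Would a count say anything at n = 32?** Exact 95% intervals are 0 to 10.9% for 0/32, 0.8 to 20.8% for 2/32 and 3.5 to 29.0% for 4/32. The chance of seeing at least one affected patient, 1 - (1 - p)^32, is 62%, 81% and 97% for assumed true rates of 3%, 5% and 10%. The intervals are wide, but the count is informative.

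**The case against.** The other side has several fair points.

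- **The plan gives more than means and medians.** SD, minimum and maximum are there too, and the minimum change shows the worst fall at each time point. That stands, but a minimum describes one patient and says nothing about how many.
- **Adverse event tables do count patients.** Protocol 12.2 makes clinically significant observations at a visit adverse events, and Protocol 12.1.1 covers abnormal vital signs that are clinically significant or need treatment. These reach the treatment-emergent tables, including those for down-titration and discontinuation. A reader might infer that a relevant fall would go uncounted everywhere, and the documents do not support that. The gap is in the vital-signs outputs. The adverse event route has no stated vital-signs criterion, may spread falls over several preferred terms, and answers a different endpoint. Laboratory and ECG significance also rests on investigator judgement, but there it is collected and tabulated for the endpoint itself.
- **The SAP follows the protocol.** A reader might take this for an SAP departure. It is not: Protocol 13.4.3 restricts incidence counts to laboratory and ECG results. The mismatch, present in both documents, is between endpoint and method.
- **The documents' blood pressure limits are not relevance criteria.** SBP 95 and DBP 50 mmHg serve eligibility and up-titration. A level is also not a change: a patient going from 97 to 94 crosses it, while one going from 150 to 100 does not. Nor would a flag for either pressure below its limit show who failed up-titration, because that criterion joins its two parts with an or. All this stands and shapes the fix.
- **The study is small and descriptive, and every value is listed.** A hand count is possible, but only once someone picks a threshold, perhaps after seeing the data.

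**Conclusion.** The concern holds as a minor reporting gap. Followed as written, the plan summarises vital signs but does not report the endpoint it names, because relevance is undefined and no vital-signs output counts patients. That conclusion rests on the text alone.

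The size is illustrative. Under the assumed baseline, SD and fall, about 2 of 32 additional patients would be below 95 mmHg. It would be tempting to read the whole 16% below that level as an effect of treatment, but about 9% would be there before any fall. Nothing in the documents shows that relevant falls are frequent, or that safety oversight depends on this table.

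**What to change.** Add one table to SAP 5.6.4 giving number and percentage of patients at each visit and time point, including baseline, by HTD and overall as SAP 4.3 prescribes. The dose-finding visits A3, B3, C3 and D3 already identify the concurrent dose. The rows would be:

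- patients below a pre-stated reporting limit who were not below it at baseline, supine and standing separately;
- patients whose orthostatic fall exceeds a pre-stated cut-off.

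The SBP 95 and DBP 50 mmHg values in exclusion criterion 2 can serve as reporting flags. The sponsor should set the final cut-offs before analysis. Percentages should use patients with a reading at that time point, because patients enrolled under protocol version 1.0 had only pre-dose readings at A1 and MPV3. A sentence in 5.6.4 should say that this table reports the endpoint and adds to the analysis in Protocol 13.4.3.

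The cost is one descriptive table from data already collected, with wide intervals at n = 32. It is reporting only and alters no eligibility, titration or stopping rule.

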### 2.2.2.2 Efficacy Endpoints

The secondary efficacy endpoints of this study are the change from baseline to visit MPV3 in:

8. Pulmonary vascular resistance (PVR), right atrial pressure (RAP), mean pulmonary artery pressure (mPAP), cardiac index (CI) and mixed venous oxygen saturation ( $S_vO_2$ ). Further haemodynamic parameters may also be calculated if considered appropriate.
9. 6-MWT, including Borg dyspnoea score
10. Biomarker (NT-proBNP)
11. Echocardiogram parameters:
  - Tricuspid regurgitation, classified as absent, mild, moderate or severe
  - Right ventricular contractibility, measured via tricuspid annular plane systolic excursion (TAPSE)
  - Pericardial effusion, classified as absent, traces or present
  - Right atrial area (end-systolic), right ventricular end-diastolic area
12. WHO functional class
13. Quality of life (SF-36v2)

### 2.2.2.3 Pharmacokinetic Endpoints

14. Apparent total clearance (CL/f)
15. Terminal half-life ( $t_{1/2}$ )
16. Apparent volume of distribution ( $V_z/f$ )

The analysis of PK parameters is covered in a reporting and analysis plan prepared by Quotient Sciences Ltd. (Appendix 4).

#### 2.2.2.4 Pharmacodynamic Endpoints

17. Percent inhibition in plasma D $\beta$ H activity (i.e. % change from baseline of D $\beta$ H activity) on visits A3/B3/C3/D3, MPV1 and MPV2 (trough samples) and to visits A1 and MPV3 (24-hour profiles)
18. Maximal and minimal observed effect on D $\beta$ H activity and time to occurrence of Emax (TEmax) and Emin (TEmin) on visit A1 (Day 1) and MPV3
19. Area under the effect-time curve (AUEC24) for % D $\beta$ H inhibition on visit A1 (Day 1) and MPV3
20. Change from baseline 24-hour urinary catecholamine levels (norepinephrine and dopamine) on visits A3/B3/C3/D3 and MPV3.

The analysis of pharmacodynamic parameters is covered in a reporting and analysis plan prepared by Quotient Sciences Ltd. (Appendix 4).

### 2.3 Overall Study Design

This is an open-label, multi-centre study in patients with PAH who are currently on stable treatment with at least one PAH medication. It is planned to evaluate the PK profile (24-hour profile and trough levels) and the safety, tolerability and efficacy of four different zamicastat doses. Each patient will start treatment with the lowest dose (50 mg zamicastat once daily) and the dose will be up-titrated to the individual **highest tolerated dose** (HTD) i.e. up to 200 mg zamicastat once daily.

A data safety monitoring board (DSMB) will periodically review the safety data and will issue a recommendation if the doses can be used as planned.

This study will consist of:

- A screening period, 5 to 12 days: visit V1
- Up to four dose finding periods, 14 days each:
  - o Dose A: visits A1, A2 and A3
  - o Dose B: visits B2 and B3
  - o Dose C: visits C2 and C3
  - o Dose D: visits D2 and D3
- Maintenance period, 42 days: visits MPV1, MPV2 and MPV3
- Follow-up period:
  - o Visit FU (down-titration): 14 days after MPV3 (only for patients taking 150 mg or 200 mg zamicastat who will not participate in the extension study)
  - o Visit FU: 14 days after last IMP intake

After confirmed eligibility, patients will initiate treatment with Dose A (50 mg zamicastat once daily) at visit A1 and will be treated with this dose level for 14 days. If Dose A was considered safe by the investigator, the patient will be up-titrated to Dose B (100 mg zamicastat once daily) at visit A3 and the patient will continue with this dosage for 14 days. Patients not tolerating Dose A have to be withdrawn from the study.

After a positive safety evaluation at visit B3, the patient will be up-titrated to Dose C (150 mg zamicastat once daily) and the patient will continue on this dose level for a further 14 days. If Dose C was tolerated by the patient, he/she will be up-titrated at visit C3 to Dose D (200 mg zamicastat once daily) where the patient will remain for 56 days (14 days dose finding period + 42 days maintenance period).

Patients not tolerating their next dose at any time during the 14-days dose finding period will come immediately to the site or call the investigator (unscheduled visit), unless intolerance was detected during a scheduled visit and the dose will be down-titrated to the patient's previous tolerated dose. Then they will continue this treatment for 42 days during the maintenance period.

The dose which will be taken during the maintenance period will be considered as an individual HTD.

At the end of the maintenance period, the patient will have the opportunity to continue treatment in an extension study (BIA-51058-202), which is described in a separate protocol.

Patients not tolerating their individual HTD during the maintenance period have to be withdrawn from the study.

## 2.4 Randomisation

No randomisation will be performed in this study.

## 2.5 Treatment

The study medication is zamicastat (BIA 5-1058). One tablet of the IMP contains 100 mg of zamicastat.

Each patient will start treatment with 50 mg zamicastat once daily (Dose A) at visit A1 and will be up-titrated step by step to the individual HTD i.e. up to 200 mg zamicastat once daily.

